1.3. Exploratory Endpoints

Analyses of each of the secondary endpoints will be provided at weeks 36 and 48, provided the item was collected.

1.4. Additional Measures

Additionally, the following measures will be provided descriptively (no inferential analyses) by study treatment arm for the safety population:

- Clinical laboratory values over time.
- Vital signs over time.
- Physical examination findings.
- Concomitant medication.

2. Analysis Strategy

No formal interim analyses of the primary endpoint were conducted, therefore the nominal α level to be used at the final analysis is 0.10 for the primary endpoint. All other secondary outcomes will also be tested at the 10% level, with no adjustment for multiplicity. Given the limited statistical power for a study consisting of 15 subjects, models will not include covariates.

2.1. Study Populations

Two study populations will be defined for these analyses:

- **Modified Intent to Treat (mITT):** The mITT analysis set consists of all subjects randomized, receiving at least one dose of treatment, and having at least one post-baseline efficacy assessment for the given parameter. No imputation techniques will be utilized for missing observations.
- Safety: The safety population consists of all subjects who were randomized and received at least one dose of the study drug.

2.2. Analyses of Primary Endpoint

The primary analysis is a comparison of the percentage of subjects with Grade 3 adverse events that begin within the first 24 Weeks following initiation of study treatment between tofacitinib and placebo. The analysis will be performed on the safety population. The test will be performed using Fisher's Exact Test, given that the largest possible number of patients affected are 10 and 5, respectively, for tofacitinib and placebo. The number and percentage of patients with at least one Grade 3 adverse event will be provided along with Clopper Pearson Exact confidence intervals for proportions at the 90% threshold.

2.2.1. Primary Analysis of the Primary Endpoint.

Proportion of patients with at least one Grade 3 adverse event within the first 24 Weeks

Analysis Set	Safety Population		
Methods	Fisher's Exact Test		
	Clopper Pearson Exact Confidence Intervals		
Results	 Number and percentage of subjects with at least one Grade 3 adverse event in the first 24 weeks 90% confidence interval for proportions P-value from Fisher's Exact Test 		

2.2.2. Secondary Analysis of the Primary Endpoint.

A sensitivity analysis will be performed to assess how the total number of Grade 3 or higher adverse events, rather than just the proportion of patients experiencing the events, affect the conclusions of the analysis of the primary endpoint. The analysis will employ Poisson Regression methodology, offset for time in the study (the lesser of 24 weeks, or withdrawal from the trial).

Analysis Set	Safety Population		
Methods	Poisson Regression offset for time in the study (the lesser of 24 weeks or		
	withdrawal from the trial)		
Dependent	Number of grade 3 or higher adverse events experienced within the first		
Variable	24 weeks on a per patient basis.		
Covariate	Treatment		
Results • Total number of Grade 3 adverse event in the first 24 week			
	 Relative risk of tofacitinib to placebo. 		
	 90% confidence interval for relative risk 		
	P-value for treatment effect		

2.3. Analyses of Secondary Endpoints

2.3.1. Analyses of the primary endpoint over time.

The secondary analyses is a comparison of the percentage of subjects with Grade 3 adverse events that begin within the first 12, 36, and 48 Weeks, respectively, following initiation of study treatment between tofacitinib and placebo. Each of the time points is a standalone analysis, utilizing the methodology described for the primary analysis of the primary endpoint in section 2.2.1

Analysis Set	Safety Population
Time Points	2.3.1a: Week 12,
	2.3.1b: Week 36,
	2.3.1c: Week 46
Methods Fisher's Exact Test	
	Clopper Pearson Exact Confidence Intervals

Results	•	Number and percentage of subjects with at least one Grade 3	
adverse event up to and including the time point of ir		adverse event up to and including the time point of interest	
	•	90% confidence interval for proportions	
	•	P-value from Fisher's Exact Test	

2.3.2. Secondary analyses of the primary endpoint over time.

Secondary analyses will be performed over time (Weeks 12, 36 and 48) using the same methodology described in section 2.2.2 to explore treatment differences in the total number of Grade 3 or higher adverse events over time. The offset for time in study will be the lesser of the withdrawal date from the trial or the time point of interest.

Analysis Set	Safety Population		
Methods	Poisson Regression offset for time in the study (the lesser of the time		
	point of interest or withdrawal from the trial)		
Time Points	2.3.2a: Week 12,		
	2.3.2b: Week 36,		
	2.3.2c: Week 46		
Dependent	Number of grade 3 or higher adverse events experienced within the time		
Variable	point of interest on a per patient basis.		
Covariate	Treatment		
Results	Total number of Grade 3 adverse event within the time point of		
interest.			
	Relative risk of tofacitinib to placebo.		
	90% confidence interval for relative risk		
	P-value for treatment effect		

2.3.3. Secondary analyses for proportion of subjects.

The proportion of subjects in the specified populations above will be compared between the two study treatment arms at the specified time points utilizing Fisher's Exact Test and Clopper Pearson confidence intervals to describe treatment differences.

Analysis Set	See Above
Time Points	See Above

Parameters	Adverse events of special interest		
	mRSS responders		
Methods	Fisher's Exact Test		
	Clopper Pearson Exact Confidence Intervals		

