Study Design	
This is a phase I/II placebo controlled study to evaluate the safety, and tolerability of tofacitinib, along with any possible efficacy descriptors, as a treatment for dcSSc. The study will enroll 15 Subjects from 18 to 70 [inclusive] years of age with dcSSc with disease duration of ≤ 60 months [from 1st non-Raynaud’s phenomenon signs or symptom]. Subjects will be randomized to tofacitinib vs placebo in a 2:1 ratio at 5 mg twice a day for 24 weeks. Subjects will also be offered to participate in an open label phase during which they will receive tofacitinib 5 mg twice a day for 24 weeks. This study will be conducted over a period of approximately 2 years. Two sites are expected to participate in this study.

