8.2 Statistical Analyses

8.2.1 Safety Outcomes

All safety analyses will be performed on the Safety Population, defined as all subjects who were randomized and received at least one dose of the study drug. Subjects will be analyzed by the treatment received.

Safety measures including AEs, clinical laboratory tests, vital signs, ECG, physical exams, and concomitant medication usage will be summarized descriptively. For quantitative variables, descriptive statistics including number of observations, mean, median, standard deviation and range will be given for the values themselves as well as for change from baseline by treatment group at each study visit. Qualitative variables will be summarized using counts and percentages by treatment group at each study visit.

The primary endpoint is the proportion of participants who experience a Grade 3 or higher adverse event at or before Week 24 and will be compared between the two treatment groups using an exact Fisher's exact test. Exact 90% confidence intervals will be calculated to estimate the incidence of the adverse events (both primary and secondary endpoints) for each treatment group. Similar methods will be used for the secondary safety endpoints. Treatment comparisons for quantitative safety outcomes will be made using two-sample t-tests or their nonparametric counterparts (e.g., Wilcoxon rank sum test). The number (counts) of adverse events will also be compared between treatments for select adverse events (e.g., Grade 3 or higher adverse events at or before Week 24, adverse events of special interest).

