8.2.2 Efficacy (Activity) and Exploratory Outcomes

The main population for efficacy and exploratory will be the modified intention-to-treat population (MITT), defined as all subjects randomized, receiving at least one dose of treatment, and having at least one post-baseline efficacy assessment. Subjects will be analyzed by assigned treatment. No adjustment for multiplicity will be made.

Similar methods (described in Section 8.2.1) to compare treatment differences in quantitative and qualitative efficacy and exploratory outcomes will be employed.

Secondary analyses will be performed to assess the robustness of the conclusions and may include the use of a secondary analysis set (e.g., the Per Protocol population (PP) consisting of all subjects in the MITT population who did not have a major protocol violation), alternative methods to deal with missing data, and alternative methods to deal with potential violations of distribution assumptions for the primary analyses. Such sensitivity analyses will be outlined in the SAP for the study.

Additional exploratory analyses may be performed and will be defined and outlined in the SAP for the study.

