1.2. Secondary Endpoints

1.2.1. Secondary Endpoint. Analyses of the Primary Endpoint Over Time.

The analyses of the primary endpoint described in sections 1.1.1 and 1.1.2 will be repeated at Weeks 12 to assess the time course of the safety profile as defined by the occurrence of Grade 3 or higher adverse events.

1.2.2. Secondary Endpoint. Analyses of the Adverse Events at the Grade 2 Threshold.

The analyses described in sections 1.1.1, 1.1.2 and 1.2.1 will be repeated for adverse events beginning at or before the time point of interest that are assessed as at least Grade 2 (moderate) severity.

1.2.3. Secondary Endpoint. % of Subjects with Adverse Events of Special Interest (AESI).

The proportion of subjects in the safety population experiencing an AESI will be compared between the two study treatment arms. Comparisons will be made for at least one AESI of any type, as well as for each of the events that are considered to be of special interest individually. Separate analyses will be performed for AESIs that occur at or before Weeks 12 and 24. AESIs are defined to be any one of herpes zoster, malignancy, serious infection, lymphocytes <500cells mm³, ANC <500cells mm³, AST > 3xULN, ALT > 3xULN, Hy's Law criteria met, Hemoglobin drop > 2mg/dL, increase in HDL/LDL ratio > 50%, or an increase in serum creatinine > 50%.

1.2.4. Secondary Endpoint. Change from Baseline in the Modified Rodnan Skin Score (mRSS).

Change from baseline in the mRSS total score will be compared between the two treatment arms to assess skin thickness relative to the initiation of study treatment at the various time points. The analysis will be performed separately at Weeks 12 and 24 on subjects in the modified intent-to-treat (mITT) population (see section 2.1).

1.2.5. Secondary Endpoint. Provisional American College of Rheumatology Combined Response Index in Systemic Sclerosis CRISS will be compared between the two treatment arms separately at Weeks 12 and 24 on subjects in the modified intent-to-treat (mITT) population (see section 2.1).

1.2.6. Secondary Endpoint. % of Responders as Defined by the mRSS.

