System Organ Class Preferred Term	Tofacitinib N=10 n (%) [1]	Placebo N=5 n (%) [1]
Total Number of Grade 3 or Higher SAEs		
Relative Risk [2]		
90% Confidence Interval [2]		
p-value [2]		

[1] Percentages are 100*n/N.

[2] Poisson Regression, offset for time in study (lesser of 36 weeks or end of study).

Table 19: TOFA Proportion of Subjects with Grade 3 (Severe) or Higher SAEs Within the First 48 Weeks. Secondary Outcome. Safety Population.

System Organ Class Preferred Term	Tofacitinib N=10 n (%) [1]	Placebo N=5 n (%) [1]
Subjects With At Least One Grade 3 or Higher Event		
90% Confidence Interval [2]		
p-value [3]		

[2] Clopper Pearson Exact confidence intervals for proportions with at least a Grade 3 SAE.

[3] Fisher's Exact Test

Table 20: TOFA Number of Grade 3 (Severe) or Higher SAEs Within the First 48 Weeks. Secondary Outcome. Safety Population.

System Organ Class Preferred Term	Tofacitinib N=10 n (%) [1]	Placebo N=5 n (%) [1]
Total Number of Grade 3 or Higher SAEs		
Relative Risk [2]		
90% Confidence Interval [2]		
p-value [2]		

[2] Poisson Regression, offset for time in study (lesser of 48 weeks or end of study).

Data cutoff date: DDMMYY

Table 21: TOFA Proportion of Subjects with Grade 2 (Moderate) or Higher SAEs Within the First 12 Weeks. Secondary Outcome. Safety Population.

System Organ Class Preferred Term	Tofacitinib N=10 n (%) [1]	Placebo N=5 n (%) [1]
Subjects With At Least One Grade 2 or Higher Event		
90% Confidence Interval [2]		
p-value [3]		

[1] Percentages are 100*n/N.

[2] Clopper Pearson Exact confidence intervals for proportions with at least a Grade 2 SAE.

[3] Fisher's Exact Test

Table 22: TOFA Number of Grade2 (Moderate) or Higher SAEs Within the First 12 Weeks. Secondary Outcome. Safety Population.

System Organ Class Preferred Term	Tofacitinib N=10 n (%) [1]	Placebo N=5 n (%) [1]
Total Number of Grade 2 or Higher SAEs		
Relative Risk [2]		

System Organ Class Preferred Term	Tofacitinib N=10 n (%) [1]	Placebo N=5 n (%) [1]
90% Confidence Interval [2]		
p-value [2]		

^[1] Percentages are 100*n/N.

[2] Poisson Regression, offset for time in study (lesser of 12 weeks or end of study).

Data cutoff date: DDMMYY

Table 23: TOFA Proportion of Subjects with Grade 2 (Moderate) or Higher SAEs Within the First 24 Weeks. Secondary Outcome. Safety Population.

System Organ Class Preferred Term	Tofacitinib N=10 n (%) [1]	Placebo N=5 n (%) [1]
Subjects With At Least One Grade 2 or Higher Event		
90% Confidence Interval [2]		

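### The Week 36 and Week 48 adverse-event comparisons labelled tofacitinib versus placebo count former placebo subjects' open-label tofacitinib events and time as placebo

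*SAP*

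**What the plan says.** **Treatment.** Randomised treatment lasts 24 weeks. The Protocol synopsis (Study Design) then states: "Subjects will also be offered to participate in an open label phase during which they will receive tofacitinib". The offer is optional, covers both arms and runs for another 24 weeks. No placebo is given after Week 24.

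**Proportions.** SAP 2.3.1 applies Fisher's exact test to Grade 3 events "that begin within the first 12, 36, and 48 Weeks, respectively, following initiation of study treatment between tofacitinib and placebo".

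**Counts.** SAP 2.3.2 uses Poisson regression with treatment as the only covariate and reports a relative risk of tofacitinib against placebo. On exposure time it says: "The offset for time in study will be the lesser of the withdrawal date from the trial or the time point of interest". The Table 20 footnote repeats this: "Poisson Regression, offset for time in study (lesser of 48 weeks or end of study").

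**Shells.** Tables 17-20 (Grade 3), 25-28 (Grade 2) and 31-32 (adverse events of special interest, AESIs) keep Tofacitinib N=10 and Placebo N=5 columns at Weeks 36 and 48, with p-values. SAP 2.4 carries the same methods to the other endpoints at those weeks.

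**Attribution rules.** For safety, Protocol 8.2.1 says: "Subjects will be analyzed by the treatment received". For efficacy, Protocol 8.2.2 says: "Subjects will be analyzed by assigned treatment". SAP 2.1 defines only who is included: "The safety population consists of all subjects who were randomized and received at least one dose of the study drug". It gives no attribution rule.

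**Status.** SAP 1.2.1 says the primary-endpoint analyses "will be repeated at Weeks 12 to assess the time course of the safety profile". SAP 1.3 and the note before the shells make Weeks 36 and 48 exploratory. Protocol 8 treats all p-values as hypothesis generating.

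**The concern.** A former placebo subject with a Grade 3 event at Week 30 had it while taking tofacitinib. The Week 36 and Week 48 tables would still place that event, and all of that subject's open-label time, under Placebo. The resulting p-value and relative risk carry the name of a contrast that the data after Week 24 no longer contain.

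Safety is the primary objective of this trial. A reader who takes the Week 48 ratio at its label would read it as the accumulated safety difference from placebo over 48 weeks. It is the difference between starting tofacitinib at once and starting it 24 weeks later.

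**Working it through.** **Attribution.** No sentence says outright that open-label events count as placebo. It follows from four features: a window that runs from first study treatment to Week 36 or 48, a two-level treatment covariate, an offset cut only at withdrawal or the time point, and a fixed Placebo N=5 column. Nothing in the SAP censors placebo subjects at the switch, splits their time or relabels the groups. Listings 3 and 5 mark phase by Day 169, and Table 1 counts an Open Label Population, but neither feeds the comparisons.

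**The plan's own figure.** The documents give no power or effect for Weeks 36 and 48. The Week 24 planning figure in Protocol 8.1 does reproduce. Exact two-sided Fisher power with 10 vs 5 subjects at alpha 0.10 is 80.2%, 80.5% and 81.0% for 20% vs 86%, 10% vs 79% and 5% vs 74%.

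**Inputs for the distortion.** From the documents: 10 vs 5 subjects, switch at Week 24, evaluation at w = 36 and 48. Assumed: a fraction f of placebo subjects continues, the rest leave at Week 24, and the tofacitinib rate is a constant R times the placebo rate.

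- Tofacitinib share of placebo-labelled time = f(w−24) / [24 + f(w−24)]
- Reported ratio = R[24 + f(w−24)] / [24 + fR(w−24)]

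For f = 1 and w = 48 the share is 24/48 = 50%. In person-weeks that is 120 of 240; at Week 36 it is 60 of 180. For R = 2 the reported ratio at Week 48 is 2×48/(24+48) = 1.33, and at Week 36 it is 2×36/(24+24) = 1.50.

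| Continuing | Week | Share on tofacitinib | R = 1.5 | R = 2.0 | R = 3.0 |
|---|---|---|---|---|---|
| 5 of 5 | 36 | 33% | 1.29 | 1.50 | 1.80 |
| 5 of 5 | 48 | 50% | 1.20 | 1.33 | 1.50 |
| 3 of 5 | 36 | 23% | 1.34 | 1.63 | 2.05 |
| 3 of 5 | 48 | 38% | 1.26 | 1.45 | 1.71 |

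With f = 1 the reported ratio cannot exceed w/(w−24) in expectation, however large R is: 36/12 = 3.0 at Week 36 and 48/24 = 2.0 at Week 48.

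**Non-constant rates.** Let the tofacitinib rate be a times placebo in a subject's first 24 weeks on drug and b times placebo in the second 24 weeks, with f = 1. Without a switch the Week 48 ratio is (24a+24b)/48. As specified it is (24a+24b)/(24+24a).

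- a = 2, b = 0.5: 60/48 = 1.25 without the switch, 60/72 = 0.83 as reported. The sign reverses.
- a = 1, b = 2: 72/48 = 1.50 in both cases. No distortion.

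**Imprecision.** Assume R = 2, a 20% placebo risk over 24 weeks (cumulative hazard −ln 0.8 = 0.223) and f = 1. SE of the log ratio = √(1/E1 + 1/E0), where E1 and E0 are the expected events.

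- Week 24: E1 = 10×2×0.223 = 4.46, E0 = 5×0.223 = 1.12. Ratio 2.0, approximate 90% interval 0.35 to 11.4.
- Week 48: E1 = 8.93, E0 = 1.12 + 5×2×0.223 = 3.35. Ratio 1.33, approximate 90% interval 0.46 to 3.8.

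**The case against.** The strongest defence is that the plan already limits reliance on these weeks. They are exploratory, go into supplemental tables, and rest on p-values that the protocol calls hypothesis generating. With 15 subjects, a reader can separate open-label events by hand from the listings, and the intervals are wide at every time point. All of this stands as to weight. None of it makes a ratio labelled against placebo estimate that quantity.

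The defence can add that the SAP is carrying out the protocol. Protocol 2.2 lists Week 36 and Week 48 adverse-event counts as secondary endpoints, and Protocol 8.2.1 extends similar methods to secondary safety endpoints. This also stands: dropping the tests would be a departure to record. Relabelling would not be.

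A reader might infer more than the documents support:

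- *That the SAP contradicts Protocol 8.2.1.* Set beside the assigned-treatment rule in 8.2.2, analysis by treatment received most naturally covers a subject given the wrong arm's drug. The protocol does not say how the rule applies after a planned switch. The gap is silence.
- *That the Week 36 and Week 48 efficacy analyses are wrong.* Tables 36 and 39-44, and Week 48 in Table 45, follow assigned treatment as Protocol 8.2.2 prescribes. At most their column label needs a change.
- *That the switch destroys power.* That compares the test with 48 weeks of placebo, which this trial never planned. At an assumed 20% vs 40% 24-week risk with constant hazards, Fisher power is 6.5% at Week 24 and 8.4% at Week 48 with the switch.
- *That Week 48 shows the narrowest intervals.* This fits the Poisson ratio only. In the same 20% vs 40% case, the expected width of the 90% Clopper-Pearson interval for five placebo subjects rises from 0.61 at Week 24 to 0.69 at Week 48.

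**Conclusion.** The point holds for the adverse-event and AESI comparisons at Weeks 36 and 48: they are immediate versus delayed tofacitinib under a placebo label. The size depends on how many placebo subjects continue and on how rates change with time on drug, neither of which the documents give. With constant rates and three to five of five continuing, a true ratio of 2.0 is reported as 1.50 to 1.63 at Week 36 and 1.33 to 1.45 at Week 48.

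A reader might conclude that the tables always err towards reassurance. That follows only under constant rates. The examples above show no distortion in one case and a reversal in another, so the direction cannot be assumed.

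The Week 12 analyses are unaffected, and the Week 24 analyses, including the primary test, are not materially affected. The harm is wrong attribution and labelling in exploratory tables. It is worth correcting, with modest weight.

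**What to change.** 1. Confine tofacitinib-versus-placebo p-values and relative risks for adverse events and AESIs to Weeks 12 and 24.
2. For Weeks 36 and 48, report adverse events descriptively by sequence (tofacitinib-tofacitinib, placebo-tofacitinib), with exposure-adjusted rates split at each subject's actual open-label start. This still delivers the counts listed in Protocol 2.2. Alternatively, keep the contrast and relabel it *immediate versus delayed tofacitinib*.
3. If a test is dropped, record it in the SAP as a departure from the similar-methods statement in Protocol 8.2.1.
4. State in SAP 2.1 how treatment received applies after Week 24.
5. Relabel the Week 36 and Week 48 columns of the efficacy tables if wanted. Their analysis can stay.

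Editorial items:

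- In Listings 3 and 5, assign phase by the actual open-label start. The ±10-day visit window puts the Week 24 dispensing visit anywhere from Day 158 to Day 178, so a fixed Day 169 can misassign phase.
- Reconcile Week 46 in the 2.3.1 and 2.3.2 method tables with Week 48 in the text.
- Settle whether Weeks 36 and 48 are secondary or exploratory.

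The cost is SAP wording, column labels in Tables 17-20, 25-28 and 31-32 (and the efficacy tables if relabelled), minor programming, and each subject's open-label start or dispensing date. The placebo-labelled Week 36 and Week 48 p-values and relative risks are lost or renamed. No protocol endpoint changes.

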2.4. Analyses of Exploratory Endpoints

Each of the items above will be analyzed for weeks 36 and 48 using the methodology described for the given time, provided the item was collected at these time points.

3. Table, Listing and Figure Shells

Note: Weeks 36 and 48 are exploratory, and will be provided in separate, supplemental tables following the reporting of primary and secondary endpoints.

3.1.1. Subject Characteristics and Study Conduct

Table 1: TOFA Subject Disposition. All Subjects

Status	Tofacitinib N (%)	Placebo N (%)
ITT Population [1]		
Safety Population [2]		
Open Label Population [3]		
Completed Study Treatment		
Discontinued Study Early		
Reason for Discontinuation		
Subject was determined to be ineligible		
Subject withdrew consent		
Investigator withdrew subject		
Study terminated by Sponsor		
Death		
Lost to follow-up		
Other		
Permanently Discontinued Study Treatment		
Reason for Discontinuation of Study Treatment		
Adverse Event		

Note: Percentages are based on the number of subjects in the Safety Population.

- [1] The ITT population includes all patients randomized to TOFA.
- [2] The Safety Population includes all randomized subjects who received at least one dose of study medication.
- [3] The Open Label Population includes all patients in the Safety Population that have completed 24 weeks (168 Days) of Double-Blind study treatment and not withdrawn from the study.

Data cutoff date: DDMMYY

Listing 1: TOFA Early Termination. ITT Subjects.

Subject ID	Treatment	Reason for Discontinuation	Time on Treatment (Days)	Time in Study (Days)

Conditional Note: No patients have discontinued as of the data cutoff date.

Table 2: TOFA Demographic Characteristics. ITT Population

Variable Statistic or Category	Tofacitinib N=10	Placebo N=5
Age (Years)		
N		
Mean		
SD		

	Tofacitinib	Placebo
Variable Statistic or Category	N=10	N=5
Median	11 20	11 0
Min, Max		
Age, n (%)		
18 to 35 years		
>35 to 55 years		
>55 to 70 years		
Gender, n (%)		
Male		
Female		
Of Childbearing Age		
Not of Childbearing Age		
Hysterectomy		
Tubal Ligation		
Post Menopausal		
Other Reason		
Ethnicity, n (%)		
Hispanic or Latino		
Not Hispanic or Latino		
Race, n (%) [1]		
American Indian or Alaska Native		
Asian		

Variable Statistic or Category	Tofacitinib N=10	Placebo N=5
Black or African-American		
Native Hawaiian or Other Pacific Islander		
White		
Not Reported		
Smoking History, n (%) [1]		
Never		
Past History		
Current Smoker		
No Response		

Note: Percentages are 100*n/N

[1] Subjects reporting more than one race are counted in each of the race categories reported.

Table 3: TOFA Baseline Characteristics. ITT Population

Variable Statistic or Category	Tofacitinib N = 10	Placebo N = 5
mRss at Baseline		
N		

Variable Statistic or Category	Tofacitinib N = 10	Placebo N = 5
Mean		
SD		
Median		
Min, Max		
Disease Duration Since 1st Non-Raynaud's Sign or Symptom (Years)		
N		
Mean		
SD		
Median		
Min, Max		
Disease Duration Since Raynaud's Phenomenon (Years)		
N		
Mean		
SD		
Median		
Min, Max		
Interstitial lung disease on HRCT of chest, N (%)		
FVC% - at Screening		
N		
Mean		

Variable Statistic or Category	Tofacitinib N = 10	Placebo N = 5
SD		
Median		
Min, Max		
DLCO% - at Screening		
N		
Mean		
SD		
Median		
Min, Max		
HAQ-DI [theoretical range, 0-3]		
N		
Mean		
SD		
Median		
Min, Max		
SHAQ: Pain From Illness in Past Week (theoretical range, 0-150)		
N		
Mean		
SD		
Median		

Variable Statistic or Category	Tofacitinib N = 10	Placebo N = 5
Min, Max		
SHAQ: Intestinal Problems Interfere with Daily Activities in Past Week [theoretical range, 0-150]		
N		
Mean		
SD		
Median		
Min, Max		
SHAQ: Breathing Problems Interfere with Daily Activities in Past Week [theoretical range, 0-150]		
N		
Mean		
SD		
Median		
Min, Max		
SHAQ: Raynaud's Interfere with Daily Activities in Past Week [theoretical range, 0-150]		
N		
Mean		
SD		
Median		

Variable	Tofacitinib	Placebo
Statistic or Category	N = 10	N = 5
Min, Max		
SHAQ: Finger Ulcers Interfere with Daily Activities in Past Week [theoretical range, 0-150]		
N		
Mean		
SD		
Median		
Min, Max		
Hemoglobin (g/dL) - at Screening		
N		
Mean		
SD		
Median		
Min, Max		
WBC (K/uL) - at screening		
N		
Mean		
SD		
Median		
Min, Max		
Large Joint Contracture N (%)		

Variable Statistic or Category	Tofacitinib N = 10	Placebo N = 5
Small Joint Contracture N (%)		
Tendon Friction Rub (Range 0 to 12) **		
